ReOpening Schools Safely and Educating Youth (ROSSEY Study) – Early Learning Ancillary Study

Clinical Trials.gov : NCT05965323

June 30, 2022

STATISTICAL ANALYSIS PLAN

1. Introduction to the SAP

This statistical analysis plan (SAP) describes the plans for statistical analyses that will address the study's protocol objectives.

2. Study Schema and objectives

Purpose:	Evaluate if risk communication health education can increase uptake of COVID-19 mitigation measures, improve children's school attendance, and increase families' physical and mental well-being using a single-arm pre/post study.
Design:	A single-arm pre/post-study
Central Hypotheses:	Our central hypotheses are that students and parents who view the risk communications will be more likely to have increased COVID-19 testing and vaccine uptake.
Primary Objectives:	
• To determine if implementing three COVID-19 education comic books for children and two COVID-19 education videos for parents will increase COVID-19 testing and vaccine uptake in children.
Secondary Objectives:	
• To determine if implementing three COVID-19 education comics books for children and two COVID-19 education videos for parents will increase physical activity, improve sleep, increase emotional regulation in children.• To determine if implementing three COVID-19 education comics books for children and two COVID-19 education videos for parents will increase physical activity, improve sleep, decrease depression and anxiety in parents
Population:	Children ages 3-5 enrolled in the Early Learning program in Yakima School District
Study Size:	Early Learning is an ancillary study with no defined sample size. We will enroll and recruit participants for a total of eight weeks
Primary Outcome Measurements:	
A. COVID-19 testing data available through self-reported surveyB. COVID-19 vaccine data available through self-reported survey
Study Duration:	11 months – September 2022- August 2023

3. Study Design

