The ancillary study runs parallel with the larger ROSSEY RCT. Recruitment, enrollment, and baseline assessment are expected to last two months (September-November 2022). Enrolled participants will not receive the comic book and parent video series until after completion of the ROSSEY RCT Post 1 follow-up Survey to not bias the data of older siblings participating in the ROSSEY RCT. A follow-up assessment for Early Learning participants is anticipated to take place 10 months after the launch of recruitment (July-August 2023)

4. Sample size and power

Early Learning is an ancillary study of 50 participants. We will enroll and recruit participants for a total of eight weeks.

Enrollment Criteria

Parent/Guardian eligibility criteria for participation in the study include:

- Must have a child attending the Early Learning Program in the Yakima School District
- Must be able to provide informed consent and legal guardian assent either virtually, on the telephone, or in-person.
- Must have a permanent mailing address available for study staff to mail necessary materials OR a working email address.

5. Population and Data Source

Participants enrolled in the ROSSEY Study: 50 children and parents from the Yakima School District. Any participants subsequently found to be ineligible will be removed. The data sources for the primary analyses are COVID testing results received from the school administration and the survey data as entered in REDCap. The COVID vaccination status data is obtained through the parent and child surveys, completed in REDCap.

6. Presentation of analyses

For each of the continuous outcomes (including the primary outcome), the mean and standard deviation will be presented pre/post intervention and p value. For binary outcomes, the percentage and frequency of children in the outcome category of interest (e.g., percentage vaccinated) will be presented pre/post and p value.

7. Outcome Definitions

a. Primary Outcomes

The two co-primary outcomes of the trial are COVID-19 testing and COVID-19 vaccine uptake. COVID-19 data are captured through school testing and self-reported survey, and COVID-19 vaccine uptake data are captured through self-reported survey. All children and parent data will be included in the intention-to-treat analysis.

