COVID-19 testing: Health reports from the school are provided for the 2022-2023 school year that list positive covid test results of study participants with the date of testing and the school of attendance. Positive test results for COVID will be a binary, yes/no variable.

COVID-19 vaccine uptake: Parents are asked at enrollment to report their vaccination status and their child's vaccination status. At post survey, the parent is asked to report if they or their child have received any COVID-19 vaccine or booster since enrollment. Vaccination status will be a binary, yes/no variable.

b. Secondary Outcomes

Secondary outcomes for the trial include the following outcomes from the PROMIS – Pediatric and Parent Proxy Instruments. The PROMIS instruments used are Children's physical activity (PA), sleep, stress, depression, and anxiety. Parents' PA, sleep, stress, depression and anxiety. The final score is represented by the T-score, a standardized score with a mean of 50 and a standard deviation (SD) of 10.

The outcome measures will be collected at pre-and post-assessment.

8. Primary exposure definition

Receiving the educational materials: three comic books and two graphic motion videos.

9. Interim analysis plan

For this study, there was no interim analysis.

10. Multiple testing

We will adjust for multiple testing by controlling FDR.

11. Missing Data

We will inspect missing data mechanisms and the amount of missing data. We will conduct an additional sensitivity analysis with multiple imputations using multivariate imputation with chained equations (MICE) approach. We will report the amount of missing data and apply appropriate methods to account for the missing data.

12. Planned Statistical Analyses

a. Baseline Demographics

The baseline characteristics of enrolled participants will be summarized in a table.

b. Efficacy Analyses Overview

Pre/post-survey outcome analyses will be conducted after all participants have been contacted and the survey is closed with missing responses marked as loss to follow-up.

- 1) **Descriptive Analyses:** Positive COVID test results will be summarized by counts. Vaccine status and COVID testing results will be presented as counts and percentages. Continuous variables will be summarized by mean, standard deviation (SD), and median (IQR). Secondary outcomes will be compared using Chi-squared tests.

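### SAP 6 plans pre value, post value and p value but no confidence interval, and the change to be reported is undefined for the co-primaries and absent for the T-scores

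*SAP*

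**What the plan says.** SAP 6 gives two reporting rules. The first reads "For each of the continuous outcomes (including the primary outcome), the mean and standard deviation will be presented pre/post intervention and p value". The second covers binary outcomes: the percentage and frequency in the "outcome category of interest (e.g., percentage vaccinated) will be presented pre/post and p value".

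The rest of the SAP bears on this as follows.

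- **SAP 7a, number of primaries:** "The two co-primary outcomes of the trial are COVID-19 testing and COVID-19 vaccine uptake".
- **SAP 7a, type of variable:** for testing, "Positive test results for COVID will be a binary, yes/no variable"; for vaccination, "Vaccination status will be a binary, yes/no variable".
- **SAP 12.b.1:** "Vaccine status and COVID testing results will be presented as counts and percentages". Continuous variables are summarised by mean, SD and median (IQR), and secondary outcomes are to be compared by chi-squared tests.
- **SAP 12.b.2:** the co-primaries are tested by chi-squared at 0.05, and pre/post changes are to be reported. The change measure is not defined.
- **SAP 12.b.3:** lists the PROMIS measures and gives no analysis.
- **Study size:** SAP 2 says "Early Learning is an ancillary study with no defined sample size", as does protocol section IV. SAP 4 and SAP 5 give 50. No power, effect size or baseline rate is stated.

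A confidence interval is mentioned in neither document.

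**The concern.** The aim is to learn whether uptake and well-being increase after the materials are distributed. That calls for an estimate of change with its precision. SAP 6 instead plans two snapshots and a p value.

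In a small pre/post study this loses information. The precision of a within-person change depends on how closely each person's two values agree. Pre and post SDs do not show that for a T-score, and pre and post percentages do not show it for a yes/no outcome. A reader who meets a non-significant p value therefore has no planned figure that shows which sizes of change remain plausible.

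The parenthesis in SAP 6 is a separate matter. It places a single primary outcome among the continuous ones, whereas SAP 7a has two primaries and both are binary.

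**Working it through.** **The plan's own figure.** The 50 participants in SAP 4 cannot be reproduced, because no effect size, baseline rate, power or dropout is given. What follows shows the precision that 50 complete pairs would bring.

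**Inputs from the SAP.** n = 50 (SAP 4); T-score SD = 10 (SAP 7b); alpha = 0.05 (SAP 12.b.2), taken as two-sided.

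**Inputs assumed.** Pre/post correlation r, the share of children who change status, the net change, baseline rates, and complete follow-up of 50. The documents give none of these.

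**1. T-scores.** Half-width of the 95% CI for mean change = t(0.975, n − 1) × 10 × √(2(1 − r)) / √n, with t = 2.01 at n = 50.

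| r | SE of mean change | 95% half-width |
|---|---|---|
| 0.3 | 1.67 | 3.36 |
| 0.5 | 1.41 | 2.84 |
| 0.7 | 1.10 | 2.20 |
| 0.8 | 0.89 | 1.80 |

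The pre and post SDs are 10 in every row. Over this range of r they leave the half-width uncertain by a factor of 3.36 / 1.80 = 1.9. If only 25 pairs were complete, the range would be 4.88 to 2.61 points.

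**2. Yes/no outcomes, half-width.** Half-width = 1.96 × √((pd − d²)/n), where pd is the proportion changing status in either direction and d is the net change. With pd = 0.20 and d = 0.10: 1.96 × √(0.19/50) = 12.1 percentage points. Keeping d = 0.10, pd = 0.12 gives 9 points and pd = 0.60 gives 21.

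**3. Yes/no outcomes, what the planned table would hide.** Suppose 15/50 (30%) before and 20/50 (40%) after. The uncorrected chi-squared p value is 0.29 and the unpaired 95% CI for the change is −8.6 to +28.6 points. The paired Wald 95% CI depends on the discordant counts:

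| Gain | Lose | Paired 95% CI (points) |
|---|---|---|
| 7 | 2 | −1.4 to +21.4 |
| 10 | 5 | −4.9 to +24.9 |
| 20 | 15 | −13.0 to +33.0 |

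The table planned in SAP 6, with two percentages, two frequencies and a chi-squared p value, is identical in all three cases.

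**4. How often a real change would be missed.** Treating 50 pre and 50 post values as independent samples, two-sided 0.05, power is 18% for 30% to 40% and 59% for 20% to 40%. The smallest rise detectable with 80% power is about 23 points from a baseline of 10%, 26 from 20%, 27.5 from 30% and 27 from 50%.

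**5. The parenthesis.** SAP 6 speaks of one primary outcome, continuous. SAP 7a has two, both yes/no. The next sentence of SAP 6 uses vaccination as its binary example, SAP 12.b.1 gives counts and percentages for both co-primaries, and SAP 12.b.2 tests both by chi-squared. One phrase stands against several.

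**The case against.** Several stronger readings are tempting and the documents do not support them.

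- **That no change estimate is planned at all.** SAP 12.b.2 commits to reporting pre/post changes for the co-primaries. What is missing there is the metric and its precision. Only for the T-scores is no within-person change planned.
- **That the main result is governed by the wrong reporting rule.** The next sentence of SAP 6 and SAP 12.b.1 and 12.b.2 all treat the co-primaries as binary. The parenthesis is a local inconsistency, and it is not the cause of the problem with precision.
- **That p values will be non-significant whatever the truth.** For a paired t test with SD 10 and n = 50, before FDR adjustment, power for a true 5-point change is 83% at r = 0.3, 93% at r = 0.5 and over 99% at r = 0.8. For 3 points it is 42%, 55% and 91%. Power is poor for small T-score changes and modest binary ones, but not for everything.
- **That a null result can never be interpreted.** From percentages and n a reader can derive the point difference and a rough unpaired interval. For T-scores, an exact unadjusted paired-t p value can be turned back into an interval: a difference of 2 with p = 0.16 gives SE = 2 / 1.427 = 1.40 and a half-width of 2.8, against 2.84 in the table above.

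The last route is not one the plan secures. SAP 12.b.1 names chi-squared tests for the secondaries, which give no interval for a mean change, and SAP 10 applies FDR control, so a published p value may be an adjusted one. For binary outcomes the paired interval cannot be rebuilt without the discordant counts.

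It is also fair to say that SAP 6 does not forbid intervals. It does not commit to them either.

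**Conclusion.** The point holds as a gap in reporting. No confidence interval is planned for any outcome, no within-person change is planned for the T-scores, and the change promised for the co-primaries is undefined. With about 50 participants and no stated power, a non-significant p value would not reliably tell no change from too little information.

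The size is 3.4 to 1.8 T-score points and about 12 percentage points as 95% half-widths at n = 50. These figures rest on r = 0.3 to 0.8, 20% discordance with a net 10-point rise, and full follow-up, all of which are assumptions. Fewer completers would widen them.

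The conflict over the primary outcome in SAP 6 is real but editorial.

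**What to change.** In SAP 6 and SAP 12.b:

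1. For each T-score, report the mean within-person change, the SD of change and a 95% CI, alongside the p value.
2. For each binary outcome, report the pre-by-post 2×2 table and the paired difference in percentages with a 95% CI (for example Tango or Newcombe paired), alongside the p value. State in SAP 12.b.2 that this difference is the change to be reported.
3. Before step 2, put the pre and post measures in SAP 7 on the same yes/no definition. Vaccination is status at enrollment but doses since enrollment at follow-up, and testing is defined as positive results over the school year. No paired difference exists until these are aligned.
4. Delete the parenthesis in SAP 6 that counts the primary outcome as continuous, so that both co-primaries fall under the binary rule.

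Items 1 and 4 cost only SAP wording. Item 2 is also wording and needs no new data once item 3 is settled; item 3 requires a decision on definitions. Any precision figures quoted in the SAP should label correlation, discordance and follow-up as assumptions.

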The ancillary study runs parallel with the larger ROSSEY RCT. Recruitment, enrollment, and baseline assessment are expected to last two months (September-November 2022). Enrolled participants will not receive the comic book and parent video series until after completion of the ROSSEY RCT Post 1 follow-up Survey to not bias the data of older siblings participating in the ROSSEY RCT. A follow-up assessment for Early Learning participants is anticipated to take place 10 months after the launch of recruitment (July-August 2023)

II. Aim 1

Evaluate if risk communication health education can increase uptake of COVID-19 mitigation measures, improve children's school attendance, and increase families' physical and mental well-being using a single-arm pre/post study.

III. Study Population

We will collaborate with the Yakima School District to recruit Early Learning students (3, 4 and 5 years old) and their parent or Guardian(s) into the research study. We will recruit Early Learning students into the study regardless of their participation in SARS-CoV-2 testing provided by the Yakima School District. This will allow us to evaluate the effect of the risk communication strategies on the uptake of SARS-CoV-2 testing and other mitigation measures.

IV. Sample Size

Early Learning is an ancillary study with no defined sample size. We will enroll and recruit participants for a total of eight weeks.

V. Enrollment Criteria

Parent/Guardian eligibility criteria for participation in the study include:

- Must have a child attending the Early Learning Program in the Yakima School District
- Must be able to provide informed consent and legal guardian assent either virtually, on the telephone, or in-person.
- Must have a permanent mailing address available for study staff to mail necessary materials OR a working email address.

VI. Study Procedures

Recruitment, Screening and Consent

Enrollment and recruitment of the Early Learning ancillary study will start the second academic year of the RCT (2022-2023). Study information in the form of a flyer will be sent home with students to parents through school email by the principal and posted on the school Parent Square site in September of 2022. In addition, ROSSEY staff will attend the Early Learning Open House to hand out study information and obtain the phone number or email address of interested parents. ROSSEY staff will follow up with interested parents and provide further information about the study.

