Risk Communication: Risk communication, in the form of comic books with accompanying read-along videos for the children (n=3) and videos for the parents (n=2) will be distributed in English and Spanish to all enrolled students within two weeks of completion of the ROSSEY RCT final assessment (December 2023). Three comic books will be distributed by mail and parents will be sent a password-protected link with the mailed comic to access the parent videos and comic book read-along videos. All intervention materials (i.e., children's comic books and parent videos) will be distributed after the final assessment of the larger ROSSEY RCT study is complete. The delay is to eliminate possible contamination of the RCT by siblings of comparison students who will receive the comic books as part of this ancillary study.

Outline of Early Learning Study Procedures

Follow-up Survey: We will contact parents 6 weeks after the risk communication intervention distribution. Parents will be asked to complete the follow-up survey either online or by phone. The surveys will ask for updates to their contact and demographic information, child's COVID-19 vaccination status, and child's SARS-CoV-2 mitigation behaviors and the secondary outcome measures.

Following the protocol from the ROSSEY RCT, the post assessment will take place over 6 weeks, allowing two weeks for final contact prior to closure. For EL participants with missing or phone numbers no longer in service, ROSSEY staff will contact the YSD to 1) determine if the student is still attending YSD, 2) find out school and teachers name to send a notice through the school to the parent letting them know we are trying to reach them. Students determined to still be enrolled at YSD, and are non-responders to the follow up survey, will receive an at home visit by ROSSEY staff as a final attempt to reach student and parent to complete survey. Follow-up assessment closure will take place one week after completion of home visits.

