- 2) **Primary Objectives:** The primary analysis of vaccine uptake and COVID testing will be conducted using a chi-squared test using $\alpha = 0.05$ and report pre/post changes over time.
- 3) **Secondary outcomes:** The secondary outcomes for the trial include measures from the PROMIS – Pediatric and Parent Proxy Instruments. The PROMIS instruments used are children's PA, sleep, stress, depression, and anxiety and parents' PA, sleep, stress, depression, and anxiety.

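### For the survey outcomes, the SAP does not require the same participants at pre and post, so selective loss to follow-up alone can shift the pre/post estimate in either direction

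*SAP*

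**What the plan says.** - **Analysis set.** SAP 7a: "All children and parent data will be included in the intention-to-treat analysis". No set of participants with both assessments is defined anywhere.
- **Display.** SAP 6 asks for a mean and SD, or a percentage and frequency, at each time. For binary outcomes these "will be presented pre/post and p value". No denominator is given for either time.
- **Test.** SAP 12b, item 2: "The primary analysis of vaccine uptake and COVID testing will be conducted using a chi-squared test using" a level of 0.05, with pre/post changes to be reported. Pairing is not mentioned. Item 1 names chi-squared tests for the secondary outcomes too.
- **Non-response.** SAP 12b runs the analysis once "the survey is closed with missing responses marked as loss to follow-up". It does not say whether the baseline values of those participants stay in the comparison.
- **Missing data.** SAP 11: "We will conduct an additional sensitivity analysis with multiple imputations" by chained equations (MICE). It also promises to look at the missing-data mechanism and to apply suitable methods, which it does not name.
- **Outcome sources.** Under SAP 7a, vaccine status comes from the surveys: status at enrollment, then any dose since enrollment. Positive tests come from school reports. SAP 2 and 7a also name self-report as a source for testing.
- **Follow-up effort.** Protocol VI, Follow-up Survey: "Students determined to still be enrolled at YSD, and are non-responders to the follow up survey, will receive an at home visit". Families who have left the district are not offered this step.
- **Size.** SAP 4: "Early Learning is an ancillary study of 50 participants". Protocol IV: "Early Learning is an ancillary study with no defined sample size".

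**The concern.** In a single-arm pre/post study, the contrast between the two columns is the whole of the efficacy evidence. If the pre column holds everyone enrolled and the post column holds those who answered, the difference mixes two things: change within participants, and a change in which participants are counted. Nothing in the design separates them. A larger sample would make the mixture more precise but would not remove it.

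Loss is foreseeable. Baseline ends in November 2022 and the earliest follow-up in the documents is July 2023. The protocol itself plans for disconnected phone numbers and for children who have left the district, and its last contact step reaches only those who stayed. If the chance of answering is related to vaccination, health or engagement, one co-primary outcome and all the PROMIS scores can move although no participant changed.

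**Working it through.** **Inputs.** From the SAP: 50 enrolled (SAP 4 and 5), α = 0.05 (SAP 12b), T-score SD of 10 (SAP 7b). The 50 comes without a baseline rate, effect size, power or dropout, so it cannot be re-derived. It affects only the p values below, not the shifts.

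The documents give no baseline vaccination rate and no retention rates, so these are assumed: 40% (20 of 50) vaccinated at baseline, with a range of retention rates. Two further assumptions are that nobody changes status and that post status is cumulative (baseline status plus any dose since enrollment). The second is needed because the post item, taken as asked, would be 0% among responders if nobody had a dose.

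**Vaccine status.** With retention rv in vaccinated and ru in unvaccinated families:

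post share = 20·rv / (20·rv + 30·ru), compared with 20/50 = 40%.

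The p value is from Pearson's chi-squared without continuity correction, treating the columns as independent.

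| rv / ru | Post | Post % | Shift (points) | p |
|---|---|---|---|---|
| 80% / 80% | 16/40 | 40.0 | 0 | 1.00 |
| 80% / 75% | 16/38.5 | 41.6 | +1.6 | 0.88 |
| 85% / 70% | 17/38 | 44.7 | +4.7 | 0.66 |
| 90% / 60% | 18/36 | 50.0 | +10.0 | 0.36 |
| 90% / 50% | 18/33 | 54.5 | +14.5 | 0.19 |
| 60% / 90% | 12/39 | 30.8 | −9.2 | 0.37 |
| 50% / 90% | 10/37 | 27.0 | −13.0 | 0.21 |

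(38.5 is an expected count.) Equal retention gives no shift. The sign follows the direction of selection.

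**T-scores.** If a fraction f is lost and their baseline mean is g points worse than that of responders, the mean appears to improve by f × g with no individual change:

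- f = 0.3, g = 5: 0.3 × 5 = 1.5 points. With SD 10 and 50 versus 35 people, the standard error is 10·√(1/50 + 1/35) = 2.20, so p is about 0.50.
- f = 0.2, g = 3: 0.2 × 3 = 0.6 points. With 50 versus 40 people, the standard error is 10·√(1/50 + 1/40) = 2.12, so p is about 0.78.

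If those lost were better at baseline, the sign reverses.

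**Can this alone give p < 0.05?** In 200,000 simulated studies per scenario, with 50 enrolled, no true change and baselines of 20%, 40% and 60%, the chi-squared test rejected in:

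- at most 0.1% at 90%/70% retention;
- 1.7% to 6.9% at 90%/50%;
- 4.0% to 15.5% at 100%/50%.

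With every vaccinated family retained, p < 0.05 needs overall loss of 52%, 36% or 26% at those three baselines, all of it among the unvaccinated.

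**Same participants in both columns.** At 90%/60%, responders are 18/36 at pre and 18/36 at post, a change of exactly 0. The same holds in every row.

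**The case against.** **The SAP never says that all enrolled are compared with responders.** True. It is silent on denominators, and reporting changes over time is compatible with within-child change. A reader might infer that the mismatch is a stated plan, but it is not. It is the natural result of an all-data rule, a test with no pairing, and non-responders marked as lost. It would also be wrong to call the two columns different people, since responders are a subset of those enrolled.

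**SAP 11 goes beyond a sensitivity analysis.** It does promise suitable methods for missing data. They are unnamed and not tied to the main comparison, so they do not repair it.

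**The vaccine illustration rests on a derivation that the SAP does not give.** This stands. Cumulative post status is an assumption, and without it the two items measure different things even in complete pairs.

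**Both co-primary outcomes are not equally exposed.** This stands. School-reported positive tests do not depend on the post survey. Testing is exposed only where it is self-reported.

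**Home visits are meant to reduce loss.** Also true. A reader might infer that loss is informative by design, or that it flatters the intervention. The protocol shows only unequal effort between families who stayed and families who left. It does not show that leaving is related to vaccination or PROMIS scores, nor in which direction.

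**Complete pairs are a choice too.** They remove the change in who is counted, but they do not make responders representative of all enrolled.

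**Conclusion.** The concern holds for vaccine status, PROMIS T-scores and any self-reported testing. The SAP leaves the pre and post sets undefined, and its inclusion rule and named test lead naturally to a comparison that can show a change when nobody changed.

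Under the assumptions above, the shift in vaccine status is +1.6 to +10 points for retention of 80%/75% to 90%/60%, and negative when selection is reversed. For T-scores it is 0.6 to 1.5 points. Baseline and retention rates, the baseline gap and cumulative post status are all assumed, so these figures show scale and do not predict the result.

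A reader might go on to infer that the study is likely to report a falsely significant result. The figures do not support that: at n = 50 the damage is mainly to the estimate, and a p value below 0.05 from this cause alone needs heavy, strongly selective loss.

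**What to change.** In SAP 6, 7a and 12b:

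1. Make the main pre/post estimate for survey outcomes the within-person change among participants with both surveys. Use a paired analysis (for binary outcomes, McNemar's test) and show pre and post values for that same set. Changing only the test would leave the displayed percentages and means on a different set from the p value.
2. Derive post vaccination status on the baseline scale: baseline status plus any dose since enrollment.
3. Add a column with the baseline values of non-responders.
4. Report the planned MICE estimate for all enrolled beside the main one.
5. Do not call the observed-pairs analysis intention-to-treat.

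The cost is SAP wording and one table column, from data already planned for collection. There are three downsides. Non-responders' baseline values leave the main pre column. Complete pairs may not represent all enrolled; the MICE estimate and the non-responder column are there to address this. Cumulative status can only move upward, so a booster in someone already vaccinated no longer counts as a change and would need its own line.

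### The school reports for the testing co-primary stop at the 2022-2023 school year, so they hold no post-intervention data if materials go out in December 2023; on the earlier schedule coverage cannot be fixed from the documents

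*SAP*

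**What the plan says.** **Source of the testing outcome.** SAP section 5 states: "The data sources for the primary analyses are COVID testing results received from the school administration and the survey data as entered in REDCap". SAP section 7a likewise names school testing and the self-reported survey together, while the schema in SAP section 2 names the survey alone. The paragraph in 7a that defines the testing variable describes only the school source: "Health reports from the school are provided for the 2022-2023 school year that list positive covid test results of study participants". It adds that the reports carry the date of each test. No section mentions reports for 2023-2024.

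**Date of exposure.** SAP section 8 defines exposure as receipt of the comics and videos. The documents time this in two ways:

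- Protocol VI, Risk Communication: materials go "to all enrolled students within two weeks of completion of the ROSSEY RCT final assessment (December 2023"). The same paragraph repeats that all materials "will be distributed after the final assessment of the larger ROSSEY RCT study is complete".
- Protocol I and SAP section 3, Study Design: "Enrolled participants will not receive the comic book and parent video series until after completion of the ROSSEY RCT Post 1 follow-up Survey". No date is given for that survey. The follow-up assessment "is anticipated to take place 10 months after the launch of recruitment (July-August 2023").

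**Gap from mailing to follow-up.** Protocol VI, Follow-up Survey: "We will contact parents 6 weeks after the risk communication intervention distribution".

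**Analysis.** SAP section 12b compares testing before and after the intervention with a chi-squared test at alpha 0.05.

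**The concern.** A pre/post comparison needs observation time on both sides of the exposure. SAP 7a fixes the school reports to one school year, and that year opens at about the time enrolment opens (September 2022). If the materials go out around December 2023, every test in those reports was taken before any family had received a comic or video. The school source could then supply a pre value but no post value.

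The primary objective asks whether the materials increase testing, and testing is one of two co-primary outcomes. With no pre and post windows written down, an analyst holding one year of reports could set them against a baseline and label the difference a post-intervention change. It would describe unexposed children.

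**Working it through.** The check is calendar arithmetic; no power or sample-size formula applies.

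**Inputs from the documents**
- School reports: 2022-2023 school year (SAP 7a).
- Later schedule: distribution within two weeks of the RCT final assessment, December 2023 (Protocol VI, Risk Communication). Taken as 1 December 2023 to 14 January 2024, which allows the month to date either the assessment or the mailing.
- Earlier schedule: follow-up in July-August 2023 (Protocol I; SAP 3).
- Mailing to follow-up contact: 6 weeks = 42 days (Protocol VI, Follow-up Survey).

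**Assumption.** The documents do not say when the 2022-2023 school year ends. I use 15 June 2023, with a range of 1 to 30 June.

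**Step 1. The plan's own figure.** September 2022 + 10 months = July 2023. This agrees with the stated July-August 2023 follow-up.

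**Step 2. Later schedule.** Post-exposure coverage = end of school year − mailing date, set to zero if negative.
- Smallest gap: 30 June 2023 to 1 December 2023 = 154 days = 22.0 weeks.
- Largest gap: 1 June 2023 to 14 January 2024 = 227 days = 32.4 weeks.
- Coverage is 0 days in every case.

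**Step 3. Earlier schedule, if the six-week gap applies.** Mailing date = follow-up date − 42 days. Follow-up from 1 July to 31 August 2023 gives mailing from 20 May to 20 July 2023.

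| Follow-up | Mailing | Year ends 1 June | 15 June | 30 June |
|---|---|---|---|---|
| 1 July | 20 May | 12 days (1.7 wk) | 26 days (3.7 wk) | 41 days (5.9 wk) |
| 15 July | 3 June | 0 | 12 days (1.7 wk) | 27 days (3.9 wk) |
| 1 August | 20 June | 0 | 0 | 10 days (1.4 wk) |
| 31 August | 20 July | 0 | 0 | 0 |

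For comparison, 1 September 2022 (taken as the start of recruitment) to 20 May 2023 is 261 days, or 37.3 weeks of pre-exposure time.

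**Step 4. Earlier schedule, if the gap does not apply.** The only anchor is then the undated Post 1 survey. Illustrative mailing dates give, for a school year ending 1 to 30 June:
- 1 March 2023: 13.1 to 17.3 weeks.
- 1 April 2023: 8.7 to 12.9 weeks.
- 1 May 2023: 4.4 to 8.6 weeks.

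**Step 5. Can the survey fill the gap as written?** For vaccination, SAP 7a states what parents are asked at enrolment and again at the post survey. For testing it gives no survey question, no recall period and no rule for combining survey with school reports. The follow-up content listed in Protocol VI covers mitigation behaviors but does not name testing.

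**The case against.** The best counter-argument is that the SAP is consistent with itself. Its study duration (September 2022 to August 2023), its July-August 2023 follow-up and its 2022-2023 reports belong together. The zero-coverage result appears only when the SAP's reporting year is set against the Protocol's December 2023 date, so it may be a by-product of the date conflict. This stands in part: if the earlier schedule is kept, the zero no longer follows automatically. But settling the date would not by itself repair SAP 7a. A December 2023 date leaves the reporting year wrong, and an earlier date still leaves the windows undefined.

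Three stronger readings are tempting, and the documents do not support them.

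- **That no schedule leaves a usable post window, or that a few weeks is the ceiling on the earlier one.** The 20 May to 20 July range takes the six-week gap from the Protocol section that carries the December 2023 date. Protocol I and SAP 3 do not state that gap, and Step 4 shows that coverage could be longer without it.
- **That the testing outcome has no post-intervention data at all.** The survey is named as a source in SAP 5 and 7a, and is the only source in the SAP 2 schema. It could supply a post value. What is missing is its definition.
- **That the plan intends to use 2022-2023 reports as the post value.** Nothing says so, and because the reports carry test dates, tests can be placed before or after mailing. The plan simply does not require this.

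**Conclusion.** The point holds for the school source. With distribution around December 2023, the reports named in SAP 7a contain no post-intervention time, and no plausible end to the school year changes that. On the earlier schedule the size is conditional. If the six-week gap applies, coverage runs from nothing to a best case of 1.7 to 5.9 weeks, depending on a school-year end between 1 and 30 June. If it does not, coverage cannot be worked out, because the Post 1 survey is undated.

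On either schedule, two gaps remain: the school reports have no pre and post windows, and the survey has no testing item or recall window. Since the school reports are the only source that the testing definition spells out, this needs correcting before the testing co-primary is analysed.

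**What to change.** 1. **Reconcile the dates.** Protocol I, Protocol VI and SAP 3 must give one distribution date and one follow-up period. Which one is for the sponsor to settle.
2. **Amend SAP 7a.** State that only tests dated after a child's mailing date count as post-intervention, and that 2022-2023 reports preceding mailing are never used as the post value.
3. **If mailing is in December 2023 and the district can supply 2023-2024 reports,** extend the reports to follow-up closure. Compare equal-length windows per child: one after mailing, and the same calendar weeks one year earlier. With six-week windows and mailing between 1 December 2023 and 14 January 2024, the post windows fall between 1 December 2023 and 25 February 2024. The comparison windows fall between 1 December 2022 and 25 February 2023, within the 2022-2023 school year and after the planned close of enrolment in November 2022.
4. **Otherwise,** take both pre and post testing from the parent survey, with the same question and recall window each time, and report the school data descriptively. This works only if both surveys carry such a question, which the documents do not show.

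**Cost.** A few sentences in SAP 7a and, under item 3, a wider data request to the district. The documents do not show that school testing or reporting continued into 2023-2024, so this must be confirmed first. Three limits should be stated in the SAP. Short windows in about 50 children (SAP 4 and 5) will hold few events. The reports as described list positive results only. A comparison with the year before matches season but does not remove year-to-year change in testing.
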